| CYP1A2 Substrates | Acetominaphen, Amitriptyline, Clomipramine, Clozapine, Cyclobenzaprine, Doxepin, Duloxetine, estradiol, Fluvoxamine, Haloperidol, Imipramine n-deme, mexiletine, nabumetone, Napqi, Naproxen, Olanzapine, Ondansetron, Phenacetin, Perfenidone, Propranolol, Riluzole, Ropivacaaine, Rucaparib, Tacrine, Theophylline, Tizanidine, Triamterene, Verapamil, Warfarin, Zileuton |
| CYP2B6 Substrates | Artemisinin, Bupropion, Cyclophosphamide, Efavirenz, Ifosfamide, Ketamine, Meperidine, Methadone, Nevirapine, Propafol, Selegine, Sorafenib, Tramadol, Velpatasvir |
| CYP2C8 Substrates | Amiodaquine, Cerivastatin, Paclitaxel, Repaglinide, Selexipag, Sorafenib, Torsemide |
| CYP2C9 Substrates | Amitriptyline, Capecitabine, Celecoxib, Clopidogrel, Diclofenac, Doxepin, Fluoxetine, Fluvoxamine, Glibenclamide, Glimepiride, Glipizide, Glyburide, Ibuprofen, Irbesartan, Lesinurad, Lornoxicam, Meloxicam, Nateglinide, Phenytoin-4-oh2, Piroxicam, Rosiglitazone, S-naproxen-nor, S-warfarin1, Suprofen, Tamoxifen, Tolbutamide, Tolbutamide1, Torsemide, Valproic Acid, Venlafaxine, Voriconazole, Zakirlukast |
| CYP2C19 Substrates | Amitriptyline, Atomoxetine, Brivaracetam, Carisoprodol, Chloramphenicol, Citaprolam, Clomipramine, Clopidogrel, Cyclophosphamide, Diazepam-nor, Doxepin, Escitalopram, Esomeprazole, Flibanserin, Hexobarbital, Imipramine-n-deme, Indomethacin, Labetalol, Lansoprazole, Moclobemide, Nelfinavir, Nilutamide, Omeprazole, Pantoprazole, Phenobarbitone, Phenytoin(o), Primidone, Progesterone, Proguanil, Propranolol, r-Methobarbital, r-Warfarin, s-Mephotoxin, Suvorexant, Teniposide, Venlafaxine, Vorconizole |

Vulnerable Subjects

We do not intend to enroll vulnerable subjects.

Subject withdrawal criteria.

Patients are free to withdraw of their own volition at any time from the study before or after surgery.

A subject may be withdrawn from the study at any time if the Investigator determines that an illness, injury, complication or adverse event requires immediate study removal, whether or not considered by the Investigator to be related to the study drug.

Subjects found to have elevated liver transaminase and/or bilirubin levels on Day 2, or Day 7 will be removed from the study.

III. METHODS AND PROCEDURES

Methods and Procedures

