Information to be recorded pre-operatively includes age, sex, height, weight, BMI, and American Society of Anesthesiology (ASA) classification. As well as baseline levels of complete blood count (CBC), chemistry profile, liver enzymes, gamma glutamate transferase (GGT), electrocardiogram, urine analysis, 12-panel urine drug test, and a urine pregnancy test.

Intra-operative information will also be recorded, including operative time, procedure, number of anchors, and complications. Patients will subsequently be stratified in different subgroups based on the procedure performed.

Pain severity scores at rest will be assessed by use of a visual analog scale (VAS; 0 = no pain, 10 = worst pain imaginable) at 6, 24, and 48 hours as well as 7 days and 14 days after surgery.

Patients will record their satisfaction with their management, on a 0-10 scale, 24 hours, 2 days and 7 days, and 14 days after surgery.

Additionally, any nausea experienced by the patients will be recorded by use of a VAS (0 = no nausea, 10 = worst nausea imaginable) at 2 days, 7 days and 14 days after surgery.

Percocet consumption will be recorded at 24 hours, 2 days and 7 days, and 14 days after surgery. Additionally, subjects will be asked to record the dates and times of CBD consumption.

Liver function tests, consisting of the standard hepatic panel, and including serum transaminase and bilirubin levels will be administered for study purposes on Day 7 and Day 14 after surgery.

Incidence of CBD-related side effects will be noted. Time to discharge from the post-anesthesia care unit (PACU) and time to discharge from the hospital will be recorded. Patients will be in the study a duration of 14 days and will be asked to fill out one online survey at the 1-year mark to determine the long-term effects that may be associated with using CBD.

In order to maintain the blinding, all data, including pain severity scores, side effects, opioid and CBD consumption, will be collected by the resident physician or physician assistant. However, if needed, in the event of an emergency or SAE, the unblinded surgeon responsible for randomization will be able to confirm whether a subject has been assigned to receive CBD or placebo.

| Study Time Points | |
|------------------------|---|

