| Day 0 - Day of Surgery | Baseline suicidality assessment (C-SSRS), Record Pain (6hrs and 24 hrs), Record clinical data during surgery and post op including time to discharge from PACU and time to discharge from the hospital, monitor for AEs |
| Day 1 | Record Pain, Opioid consumption, CBD consumption, Satisfaction, monitor for AEs |

The use of cannabidiol (CBD) in pain reduction and opioid use after shoulder arthroscopy. A Double-Blind, Randomized Control Study

Version 06/28/2022

| | |
|-----------------------------------|--|
| Day 2 | Record Pain, Opioid consumption, CBD consumption, Satisfaction, Nausea, monitor for AEs |
| Day 7 - Standard of Care Visit 1 | Record Pain, Opioid consumption, CBD consumption, Satisfaction, Nausea, Liver Function Tests - Non-standard of care, C-SSRS, Drug accountability, monitor for AEs |
| Day 14 - Standard of Care Visit 2 | Record Pain, Opioid consumption, CBD consumption, Satisfaction, Nausea, monitor for AEs Liver Function Tests - Non-standard of care, C-SSRS, Drug accountability and review of completed subject diary, monitor for AEs |
| Month 12 – Post-Trial Survey | Record Pain; Complete ASES, KJOC Shoulder, and SANE assessment |

Data Analysis and Statistical Plan

Our power analysis was based on the literature of post-operative pain control following shoulder arthroscopy. Under the assumption of a VAS of 3 and 1.8 for the control and CBD respectively, with a SD of 2: Group sample sizes of 45 in each group would achieve 80% power to reject the null hypothesis of equal means when the population mean difference between Control and CBD is $\mu_1 - \mu_2 = 3.0 - 1.8 = 1.2$ with a standard deviation for both groups of 2.0 at a significance level (alpha) of 0.05 using a two-sided two-sample equal-variance t-test. Thus, to allow for a 5% drop-out at 14-day follow-up, 100 patients would be required to enroll.

For descriptive statistics, categorical values will be described by percentages, and continuous variables will be described by means with standard deviations. To compare primary and secondary outcomes, a T-Test will be performed, with a p-value of 0.05 set to determine statistical significance. Testing will be performed to determine whether sample distribution is normal; if not, non-parametric testing will be performed.

Analysis of the Primary Efficacy Endpoint(s)

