To compare primary outcomes (VAS score), a T-Test test will be performed, with a p-value of 0.05 set to determine statistical significance. Testing will be performed to determine whether sample distribution is normal; if not, non-parametric testing will be performed. Patients who do not complete at least 80% of follow-up visits will be considered lost to follow-up and will not be included in the analysis.

Analysis of the Secondary Endpoint(s)

To compare secondary outcomes (opioid use, satisfaction), complication rates), a T-Test will be performed, with a p-value of 0.05 set to determine statistical significance. For categorical variables, a Fisher's exact test will be performed. Testing will be performed to determine whether sample distribution is normal; if not, non-parametric testing will be performed. Patients who do not complete at least 80% of follow-up visits will be considered lost to follow-up and will not be included in the analysis.

Data and Safety Monitoring Plan

Data monitoring will be done by [name], the principal investigator will oversee the conduct of the study. He will review enrollment, accumulated study data, including pain VAS scores, Percocet consumption VAS scores, liver function test results, adverse events, protocol deviations, study compliance and data accuracy quarterly.

He will monitor whether or not:

1. Collection and storage of patient data was performed in a sensitive and secure manner, as defined in the informed consent form and protocol, ensuring information is stored on REDCap.
2. All study activities were conducted with primary emphasis on patient care and wellbeing, ensuring the patients are not in discomfort and have an abnormally high VAS following the surgery.
3. If there were any adverse events, and if so were addressed appropriately and per protocol
4. The risk/benefit to patients has remained the same throughout the course of the study.

The study will be stopped if there are unexpected severe adverse events in more than one patient. Adverse Events (AEs) will be defined as negative reactions to the CBD treatment. We will submit summaries of data and safety monitoring to the IRB annually. De-identified primary and secondary outcome data will be shared by the participating site PI quarterly, and they will notify the host site PI ([name]) upon each enrolled patient.

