- **Unlikely to be related** – A clinical event, including an abnormal laboratory test result, whose temporal relationship to drug administration makes a causal relationship improbable (e.g., the event did not occur within a reasonable time after administration of the trial medication) and in which other drugs or chemicals or underlying disease provides plausible explanations (e.g., the participant's clinical condition, other concomitant treatments).

Not Related – The AE is completely independent of study drug administration, and/or evidence exists that the event is definitely related to another etiology. There must be an alternative, definitive etiology documented by the clinician.

The occurrence of an AE or SAE may come to the attention of study personnel during study visits and interviews of a study participant presenting for medical care, or upon review by a

study monitor. All AEs including local and systemic reactions not meeting the criteria for SAEs will be captured on the appropriate RF. Information to be collected includes event description, time of onset, clinician's assessment of severity, relationship to study product (assessed only by those with the training and authority to make a diagnosis), and time of resolution/stabilization of the event. All AEs occurring while on study must be documented appropriately regardless of relationship. All AEs will be followed to adequate resolution.

Any medical condition that is present at the time that the participant is screened will be considered as baseline and not reported as an AE. However, if the study participant's condition deteriorates at any time during the study, it will be recorded as an AE. UPs will be recorded in the data collection system throughout the study.

Changes in the severity of an AE will be documented to allow an assessment of the duration of the event at each level of severity to be performed. AEs characterized as intermittent require documentation of onset and duration of each episode.

The PI will record all reportable events with start dates occurring any time after informed consent is obtained until 7 (for non-serious AEs) or 30 days (for SAEs) after the last day of study participation. At each study visit, the investigator will inquire about the occurrence of AE/SAEs since the last visit. Events will be followed for outcome information until resolution or stabilization.

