Planned safety monitoring during the duration of the study will include monitoring for liver function, laboratory abnormalities and suicidality assessments throughout the study and for follow-up visits. Liver function tests, including serum transaminase and bilirubin, will be obtained on Day 2, Day 7, and Day 14. Elevated liver transaminase and bilirubin levels will be grounds for immediate removal from the study. C-SSRS will be assessed at baseline, Day 7, and Day 14 by the surgeon. Although CBD does not increase risk of suicidal ideation and behavior, this is being done in accordance with FDA recommendation for clinical trials involving drugs with CNS activity. If subjects are found to pose a risk to themselves, standard institutional procedures will be followed to refer subjects for appropriate care, including emergency care if needed.

The maximum CBD dose given to any subject will be less than 2mg/kg/day, well below levels associated with any hepatic risk (Iffland & Grotenherman, 2017).

The use of cannabidiol (CBD) in pain reduction and opioid use after shoulder arthroscopy. A Double-Blind, Randomized Control Study

Version 06/28/2022

CBD was not deemed to increase the severity of Percocet's opioid toxicities, as they act on different pathways. There is a potential for CBD to work in the same C450 cytochrome pathway as the acetaminophen, and thus no additional acetaminophen is to be prescribed outside of this, which is well below the maximum prescribing threshold of 4g per day.

The patients will stay in the recovery unit until cleared for discharge by an anesthesiologist. They will be prohibited from driving or operating a motor vehicle for 2 hours following their first dose of the study drug.

Patients will be educated on the importance of keeping the study drug in a safe place at all times and ensure it is not accessible to anyone other than themselves.

Additionally, all patients will be de-identified and given a code. Information linking the patient codes to the participants' names and medical record numbers will be stored in a secure location separate from the medical information. Access to the information linking the linkage codes with participant identifiers shall be restricted.

Potential Benefits to the Subjects

Patients may experience less pain post-operatively, and may require less narcotics use, which has a steeper side-effect profile. However, these benefits cannot be guaranteed.

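### Raised liver tests remove the patient from the study rather than only from study drug, so scheduled outcome data that could be kept cheaply are lost

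*Combined protocol and SAP*

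**What the plan says.** Section II, Subject withdrawal criteria, sets a mandatory rule: "Subjects found to have elevated liver transaminase and/or bilirubin levels on Day 2, or Day 7 will be removed from the study". Section IV, Protection against Risks, has a similar rule in different terms: "Elevated liver transaminase and bilirubin levels will be grounds for immediate removal from the study". The first is triggered by either analyte; the second, read literally, needs both and speaks of grounds.

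Section II also gives a discretionary route: "A subject may be withdrawn from the study at any time if the Investigator determines that an illness, injury, complication or adverse event requires" immediate removal. That too is removal from the study.

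The two sections on testing disagree about Day 2. Protection against Risks says liver tests "will be obtained on Day 2, Day 7, and Day 14". Methods and Procedures says they "will be administered for study purposes on Day 7 and Day 14 after surgery", and the Study Time Points table lists none on Day 2.

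Days 7 and 14 are both routine clinic visits; the table labels the second "Day 14 - Standard of Care Visit 2". The analysis sections add: "Patients who do not complete at least 80% of follow-up visits will be considered lost to follow-up", and such patients are left out of the analysis. For adverse events, recording runs "until 7 (for non-serious AEs) or 30 days (for SAEs) after the last day of study participation", and events are followed until they resolve or stabilise.

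**The concern.** Stopping the tablets deals with the hepatic risk. Ending participation as well gives no further protection, and it ends outcome collection in the patients who have shown a liver signal. Nothing in the plan describes a patient who is off study drug but still followed for pain, opioid use, satisfaction, nausea, C-SSRS or the scheduled liver panel.

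The triggering event occurs after randomisation and may be related to treatment, since the Risk section lists hepatic toxicity among the rare effects of CBD. Missing outcomes could therefore be unequal between arms. The 80% rule can widen the gap from the missing Day 14 values to the whole patient. The plan has no as-randomised analysis rule and no missing-data method that would repair this.

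**Working it through.** **1. Planned power.** Inputs from Data Analysis and Statistical Plan: difference 1.2, SD 2.0, two-sided alpha 0.05, equal-variance t-test, 45 per group. The noncentrality is 1.2 / (2.0 × √(2/45)) = 2.846 on 88 degrees of freedom, which gives power 80.4%. The plan's 80% reproduces. With 100 enrolled and 5% drop-out there are 100 × 0.95 / 2 = 47.5 per arm, noncentrality 2.924 and power 82.5%. That is the comparator below.

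**2. What a removal costs.** Pain is due at 6, 24 and 48 hours, Day 7 and Day 14 (five time points). Post-operative data days are Days 1, 2, 7 and 14 (four days). The plan does not define follow-up visits for the 80% rule, so both counts are shown.

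| Removal | Scheduled data lost | By day | By pain time point |
|---|---|---|---|
| Day 7 | Day 14 | 3/4 = 75%, excluded | 4/5 = 80%, kept |
| Day 2 (only if a test is drawn) | Days 7 and 14 | 2/4 = 50%, excluded | 3/5 = 60%, excluded |

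The documents do not say whether a removed patient still receives the 1-year survey.

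**3. Adverse-event capture.** If the removal day is the last day of participation, non-serious events are recorded to Day 7 + 7 = Day 14, or Day 2 + 7 = Day 9. Serious events are recorded to Day 7 + 30 = Day 37, or Day 2 + 30 = Day 32. An abnormal result that leads to withdrawal is itself an adverse event under Adverse Event Reporting. The safety loss is therefore mainly the scheduled C-SSRS and liver panel.

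**4. Illustrative removal rate.** No threshold for an elevated result is given, so the following are assumptions: normal-scale AST, ALT and bilirubin; AST/ALT correlation 0.6; bilirubin independent; all three within the limit at baseline; serial correlation 0, 0.5 or 0.8. Simulating 2,000,000 patients gives these rates of chance elevation:

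- Any analyte above the 97.5th percentile, Day 7 test only: 6.8%, 5.6%, 3.9%.
- Any analyte above the 99.5th percentile, Day 7 test only: 1.4%, 1.3%, 0.9%.
- A transaminase and bilirubin both above the 97.5th percentile: about 0.04-0.1% with Day 7 only, and 0.07-0.2% if Day 2 is also tested.

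Chance elevations fall on both arms alike. They cost data but do not by themselves bias the comparison.

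**5. Illustrative power.** This assumes that every removed patient leaves the analysed comparison and that removals add to the 5% drop-out. Day 7 test only, any analyte, 97.5th percentile:

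- 3.9% removed: 100 × (1 − 0.05 − 0.039) = 91.1, taken as 91, or 45.5 per arm; power 80.8%.
- 6.8% removed: 100 × (1 − 0.05 − 0.068) = 88.2, taken as 88, or 44 per arm; power 79.5%.

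The loss from 82.5% is 1.7 to 3.0 points. It arises only with a Day 14 endpoint, or with a visit count that puts the patient under 80%. For a pain endpoint at or before Day 7 with the 4/5 count, the score is already in hand and the patient is kept, so nothing is lost. Under the literal both-analytes reading, fewer than one patient in 100 is removed and the loss is near zero.

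**The case against.** The strongest reply is that the practical effect may be negligible. Protection against Risks names transaminase and bilirubin together and speaks of grounds, which is narrower and arguably permissive. The plan names no primary VAS time point, and three of five pain scores are due by Day 2 and four by Day 7. Patients with abnormal LFTs are excluded at entry, and hepatic toxicity is listed only as rare. Adverse-event follow-up continues. Part of the harm comes from the 80% rule rather than from the removal rule. A sponsor might also legitimately be interested in pain while on an as-needed drug.

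Most of this stands as a limit on size. It does not remove the point. The rule in Subject withdrawal criteria is mandatory and triggered by either analyte, and the Day 7 test is scheduled in every version of the testing plan. The stated dose ceiling of under 2 mg/kg/day does not rule out a treatment-related rise: 25 mg every 4 hours around the clock is 6 × 25 = 150 mg/day, which reaches 2 mg/kg/day at 75 kg or less. The on-treatment question concerns which analysis is primary. Data collected after drug is stopped can be set aside for an on-treatment analysis, but data never collected cannot be recovered for an as-randomised one.

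**Conclusion.** The point holds as a cheap improvement. Confidence is high that the wording ends outcome follow-up, and much lower about how much that matters. The definite loss per Day 7 removal is one full set of Day 14 assessments. Exclusion of the whole patient follows under one visit count and not the other. The power figures are illustrations resting on the assumptions listed with them.

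A reader might infer four stronger things that the documents do not support:

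- **That removed patients leave safety monitoring.** Adverse events are still recorded and followed.
- **That the pain comparison is biased in a known direction.** Unequal loss is possible, but its rate and effect cannot be derived from the plan.
- **That the trial is underpowered because of this rule.** Even the less favourable figure for the scheduled Day 7 test is 0.5 points under 80%, and plausible readings give no loss.
- **That Day 2 removals will occur.** They require a test that Methods and Procedures and the time-point table do not schedule.

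**What to change.** In Subject withdrawal criteria and in Protection against Risks, replace removal from the study with wording such as: *study drug is stopped; all scheduled assessments through Day 14 and the 1-year survey continue unless the patient withdraws consent to follow-up.* Use the same wording where the Investigator stops drug for an adverse event. Record the date and reason. In the analysis sections, keep these patients in their randomised arm for the main analysis and exempt them from the 80% exclusion; an on-treatment analysis can be supplementary. The level at which drug must be stopped remains the sponsor's clinical decision.

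The cost is a protocol and consent wording amendment and one CRF field. Days 7 and 14 are already standard-of-care visits, the study liver panels are already planned for every patient, and the 1-year outcome is a single online survey. The downside is that some off-drug data enter the comparison.

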shoulder arthroscopy who receive post-operative CBD and a placebo group. Patients will be asked on postoperative Day 1, 2, 7, and 14 to rate their pain according to the VAS scale. Additionally, opioid consumption, CBD consumption, as well as patient satisfaction will be measured. Patients will be asked in the post-trial period to fill out a questionnaire pertaining to 1-year outcomes. The questionnaire will be in the form of a single online survey including ASES score, VAS score, KJOC Shoulder score, and SANE score.

Rationale for multi-center study:

The second site is essential for this project, for both recruitment and logistical purposes. While NYULOH does have high-volume, a large proportion of these patients will be ineligible due to the exclusion criteria and will not want to participate given that this is a randomized, controlled, double blinded study. Additionally, the second site PI was absolutely instrumental in the conceptualization and the design of this study, as well as securing the necessary funding for it happen. This study would not be feasible without their collaboration. Additionally, the second site PI has an academic appointment here at NYU Langone, and is instrumental in the education of the trainees here at our institution

Primary Objective

The primary objective of the study is to determine if there are any differences in post-operative pain between patients receiving CBD after shoulder arthroscopy compared to patients who do not receive it.

Secondary Objective

Secondary objective of the study is to determine if there are any differences in patient satisfaction, the incidence of opioid induced nausea, and the numbers of opioids and CBD/placebo ODTs consumed by the two patient cohorts.

II. CHARACTERISTICS OF THE RESEARCH POPULATION

Number of Subjects

We will aim to enroll a total of 100 subjects (50 per cohort) as determined by the priori sample size calculator.

Gender of Subjects

Men and women will be included in this study.

Age of Subjects

Subjects included study will be aged 18-75 years, inclusive.

Racial and Ethnic Origin

There are no enrollment restrictions based on race or ethnic origin.

Inclusion Criteria

Patients will be screened for eligibility using the following criteria. All study subjects must meet the following inclusion criteria:

- Patients undergoing an arthroscopic shoulder procedure (rotator cuff repair, decompression, labrum repair)
- Patients ages 18-75, inclusive

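### The liver rule takes a patient out of the study rather than off the ODT, and the 80% visit rule can then drop that patient from the analysis

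*Combined protocol and SAP*

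**What the plan says.** Two places set the liver rule. Section II, Subject withdrawal criteria: "Subjects found to have elevated liver transaminase and/or bilirubin levels on Day 2, or Day 7 will be removed from the study". Section IV, Protection against Risks: "Elevated liver transaminase and bilirubin levels will be grounds for immediate removal from the study". Both act on study participation. Neither offers stopping the ODT with continued follow-up.

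The test days differ between sections. Protection against Risks says: "Liver function tests, including serum transaminase and bilirubin, will be obtained on Day 2, Day 7, and Day 14". Section III, Methods and Procedures, says the tests "will be administered for study purposes on Day 7 and Day 14 after surgery", and the Study Time Points table also lists them on those two days only.

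The primary and secondary endpoint analysis sections share one exclusion rule. Patients who do not "complete at least 80% of follow-up visits will be considered lost to follow-up and will not be included in the analysis". No exception is made for removals that the protocol requires, and the plan does not define which contacts count as follow-up visits. Study Design gives one list: "Patients will be asked on postoperative Day 1, 2, 7, and 14 to rate their pain according to the VAS scale". Methods and Procedures gives another for pain: "at 6, 24, and 48 hours as well as 7 days and 14 days after surgery".

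For safety, Adverse Event Reporting provides that "Events will be followed for outcome information until resolution or stabilization". No comparable sentence covers the pain scores or Percocet counts of a removed patient.

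**The concern.** A laboratory result obtained after randomization can decide whether a randomized patient enters the pain and opioid comparisons. Section IV, Risk, lists hepatic toxicity among the rare side effects of oral CBD, so the result may be related to treatment and the exclusions need not fall equally on the two arms. If they do not, and if the excluded patients differ in pain from the others, the comparison is no longer the one that randomization set up. An excluded patient also loses valid scores already recorded.

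The safety aim does not require this. Stopping the ODT ends exposure just as quickly, and the patient can still report pain and opioid use on the days already scheduled.

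**Working it through.** **The plan's own figure.** Inputs from Data Analysis and Statistical Plan: means 3.0 and 1.8 (difference 1.2), SD 2, two-sided alpha 0.05, equal-variance t-test. The exact noncentral t calculation gives power 0.8037 at 45 per group and 0.7947 at 44, so the stated 45 per group reproduces. With 5% drop-out, 90/0.95 = 94.7, so 95 are needed and 100 are planned. The sample size is not in dispute.

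**Share of visits completed.** Share = contacts up to and including the removal day / contacts scheduled, compared with at least 80%. The removal-day record is counted and no other contact is missed, which is the most favourable case for staying in. These counts lie within the 14-day trial:

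| Contacts counted | Source | Removed Day 2 | Removed Day 7 |
|---|---|---|---|
| Days 1, 2, 7, 14 | Study Design | 2/4 = 50%, out | 3/4 = 75%, out |
| Clinic visits, Days 7 and 14 | Study Time Points | 0/2 = 0%, out | 1/2 = 50%, out |
| 6 h, 24 h, 48 h, 7 d, 14 d | Methods and Procedures | 3/5 = 60%, out | 4/5 = 80%, kept |
| Days 0, 1, 2, 7, 14 | Study Time Points | 3/5 = 60%, out | 4/5 = 80%, kept |

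A Day 2 removal is out on all four counts, but it can occur only if the Day 2 test is drawn. A Day 7 removal is out on two and kept on two. Where kept, it sits exactly at the limit: one other missed contact gives 3/5 = 60%. A kept Day 7 removal still has no Day 14 score.

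**Illustrative size.** The documents give no cut-off for an elevated result and no expected rate, so these inputs are assumptions: k = 1 to 3 more removals in one arm of 50 than in the other, and a mean pain gap d = 1 to 2 points between the removed patients and the rest of their arm. Shift in the difference between arms = (k/50) × d:

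| k | d = 1 | d = 2 |
|---|---|---|
| 1 | 0.02 | 0.04 |
| 2 | 0.04 | 0.08 |
| 3 | 0.06 | 0.12 |

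Against the planned difference: 0.02/1.2 = 1.7% and 0.12/1.2 = 10%. The standard error of the difference at the planned size is 2 × √(2/45) = 0.42, so the shift is 0.02/0.42 = 0.05 to 0.12/0.42 = 0.28 standard errors. Removals that are equal in number in both arms, with the same pain gap, shift nothing.

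**Power.** Starting from 50 v 50 (power 0.844), losing 2, 5 or 10 CBD patients gives 0.836, 0.824 or 0.799. Power is not the issue at any plausible number.

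**The case against.** The strongest reply is that this will rarely happen. Entry criteria exclude abnormal liver tests, cirrhosis and Child-Pugh B or C impairment. The protocol calls hepatic toxicity rare and states a dose ceiling below levels linked to hepatic risk. Every patient in both arms receives acetaminophen through Percocet, so liver rises may occur in either arm. Nothing in the documents links a liver rise to pain. All of this stands. It is why the size is called small and assumed, and why a difference between arms is described as possible, not shown.

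A second reply is that the underlying fault is the 80% rule, which drops any randomized patient with too few visits, including one who withdraws by choice. That is fair. Analysing every randomized patient would make a special exception unnecessary. It would not supply the pain and opioid records that are never collected once a patient is removed, so the change from removal to stopping the ODT is needed either way.

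A reader might infer that a Day 7 removal is excluded on most counts. That holds only if the Month 12 survey is counted as a visit, which adds 3/5 = 60% and 4/6 = 67%. Study Design and the Study Time Points table place that survey after the trial, and Methods and Procedures sets participation at 14 days. Without it, the split is even.

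A reader might also infer from the word *and* in Protection against Risks that a patient with an isolated rise stays on drug. The sentence can be read as a list, with the *and/or* of the withdrawal criteria governing. It is a wording fault to tidy, not evidence of a different rule.

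**Conclusion.** The point holds and is minor. As written, a possibly treatment-related event removes a patient from follow-up, and the 80% rule may then remove that patient from the primary and secondary analyses. For Day 2 this is certain, provided the Day 2 test is drawn. For Day 7 it depends on a visit count the plan leaves undefined.

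The documents do not support saying that the result would be biased for or against CBD, because the removal rate, its difference between arms and the pain level of removed patients are all unknown. The 0.02 to 0.12 point range rests wholly on the assumed excess and pain gap. Nor do they support saying that removed patients lose safety follow-up, since the adverse event rules cover the liver finding. The case for change is that it costs little and closes an avoidable exclusion after randomization.

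**What to change.** 1. In Subject withdrawal criteria and Protection against Risks, replace removal from the study with: *will stop the study ODT at once and remain in follow-up for all remaining scheduled pain, opioid and liver assessments*. Use *and/or* for the trigger in both places. Leave the investigator's power to withdraw a subject for safety as it is.
2. In the primary and secondary endpoint analysis sections, add: *Subjects who stop the ODT under the liver rule or for another adverse event are analysed in their randomized group with all recorded scores; the 80% visit rule does not exclude them.*
3. Make the Day 2 liver test consistent. Either add it to Methods and Procedures and the Study Time Points table or, if the sponsor confirms it is not drawn, take it out of the withdrawal criteria and Protection against Risks.

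The cost is a protocol amendment with short wording edits. Day 7 and Day 14 visits and liver tests are already scheduled. A Day 2 draw, if kept, needs a place to be taken, because the table labels only Days 7 and 14 as visits. The statistical downside is that some analysed scores will come from after the ODT was stopped, which may slightly dilute a true effect. The required sample size stays at 45 per group.
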